### 3. Purpose and contents of clinical trials

#### 3.1 Purpose

The purpose of this trial is to evaluate the safety and effectiveness of the SAPIEN 3 transcatheter heart valve implantation (TAVI) in Chinese patients with symptomatic severe calcific aortic stenosis who are considered at high risk for surgical valve replacement. Clinical data will be submitted for the purposes of obtaining Chinese regulatory approval.

#### 3.2 Contents

This is a prospective, single-arm, multi-center study to assess the safety and effectiveness of the SAPIEN 3 THV. A minimum of 50 patients (maximum of 60 patients) with symptomatic severe calcific aortic stenosis requiring transcatheter aortic valve implantation (TAVI), who are considered high risk for surgical valve replacement and who receive a SAPIEN 3 THV.

Study endpoints include:

##### Primary Endpoint

The primary endpoint is all-cause mortality at 30 days post-index procedure.

##### Secondary Endpoints

##### Safety Endpoints

- Cardiovascular and non-cardiovascular mortality at 72 hours (peri-procedural) and 30 days
- Stroke at 30 days
- TIA at 30 days
- All-cause mortality & disabling stroke at 30 days
- Vascular complications (major) at 30 days
- Bleeding complications (life threatening or disabling, and major) at 30 days
- Myocardial infarction at 30 days
- Acute kidney injury at 30 days (stages II and III)
- Coronary obstruction requiring intervention at 30 days
- Arrhythmia and conduction disturbance at 30 days
- Permanent pacemaker implantation at 30 days
- Valve-related dysfunction requiring repeat procedure (BAV, TAVI or SAVR) at 30 days

- Mitral valve apparatus damage or dysfunction at 30 days
- Unplanned use of cardiopulmonary bypass (CPB) during TAVI implant procedure
- Pericardial tamponade at 30 days
- Endocarditis at 30 days
- Valve thrombosis at 30 days
- Valve malposition (migration, embolization, and ectopic deployment) at 30 days
- Ventricular septal perforation at 30 days

#### Device and Procedure Success Composite

- Absence of procedural mortality AND
- Correct positioning of a single prosthetic heart valve into the proper anatomic location AND
- Intended performance of the prosthetic heart valve (no prosthesis-patient mismatch and mean aortic valve gradient <20mmHg or peak velocity <3m/s, AND no moderate or severe prosthetic valve regurgitation) at 30 Days

#### Efficacy

- New York Heart Association (NYHA) Classification at 30 days
- Hemodynamic valve performance evaluation by echocardiography for aortic valve stenosis and aortic valve regurgitation (paravalvular & central) at 30 Days as determined by Echo core lab

#### Quality of Life

- KCCQ at 30 days

### 4. Background information of clinical trials

Prolonged average life expectancy has resulted in an aging population and consequently, an increase in the number of patients with acquired, calcific, severe, symptomatic aortic stenosis (AS). The standard of care therapy for patients suffering from severe AS is aortic valve replacement surgery (AVR). In the aged population, many patients are too sick to be operated or have co-morbidities that preclude the option for surgery [1].

AS is a progressive, debilitating and life-threatening disease if left untreated. Affected individuals are typically > 65 years of age. The pathology involves progressive calcification of the leaflet bodies which limits normal cusp opening during systole. Cellular aging and degeneration have been implicated in this form of the disease and diabetes mellitus and hypercholesterolemia are risk factors.

#### Disease Process

The pathophysiology of AS includes an increase in afterload, progressive hypertrophy of the left ventricle, and a decrease in systemic and coronary blood flow as consequences of valve obstruction. Typically, patients with AS are free from cardiovascular symptoms (e.g. angina, syncope and/or heart failure) until late in the course of the disease. However, once symptoms manifest, the prognosis is poor, especially when associated with congestive heart failure.

Death in general, including sudden death, occurs primarily in symptomatic patients. Survival analyses have demonstrated that the interval from onset of symptoms to time of death is approximately two years in patients with heart failure, three years in those with syncope, and five years in those with angina [2]. Among symptomatic patients with moderate-to-severe AS treated medically, mortality rates after the onset of symptoms were approximately 25% at 1 year and 50% at 2 years and more than 50% of deaths were sudden [3].

Grading the severity of AS is based on a variety of hemodynamic and natural history data. According to the ACC/AHA guideline authors, AS is best described as a continuum. In patients with moderate-to-severe AS, valve area may decline up to 0.3 cm^2 per year and the systolic pressure gradient across the valve can increase by as much as 15-19 mmHg per year, with a higher rate of progression observed in elderly patients with coronary artery disease

(CAD) and chronic renal insufficiency [4]. Relief of aortic valve obstruction typically results in an improvement of symptoms, hemodynamic parameters, and global left ventricle systolic function, as well as reversal of left ventricular hypertrophy [4,5].

#### Alternative Therapies/Techniques

Treatment options for patients suffering from symptomatic aortic stenosis, prior to the introduction of transcatheter aortic valve implant (TAVI), included palliation of symptoms without valve replacement (non-surgical standard therapy), or surgical aortic valve replacement (AVR). Treatment options were determined by patient risk for morbidity or mortality after surgery and patient choice. Non-surgical treatment options, including balloon aortic valvuloplasty, did not provide sustained hemodynamic improvement and have led to poor quality of life and shortened life expectancies [5-7]. Patients considered poor candidates for AVR typically present with significant multiple morbidities or anatomical limitations [8].

Patient frailty may also contribute to the decision to forego surgery. Surgical AVR has demonstrated excellent long term outcomes for patients with aortic valve stenosis, even in high risk populations (STS PROM > 10) [5-7, 9-11].

#### Transcatheter Aortic Valve Implantation (TAVI)

Transcatheter aortic valve implantation (TAVI) was first performed in man in 2002 [12], followed by clinical trials and approval for commercialization in Europe in 2007 [13, 14]. It is currently estimated that approximately 300,000 patients have undergone TAVI worldwide. The Edwards THV global clinical research program includes more than 30,000 patients enrolled in 18 clinical studies that include first-in-man, feasibility, and pivotal studies as well as randomized controlled trials and post market registries. Results and outcomes from these trials have been publically reported at medical congresses and in peer-reviewed scientific journals [15-22]. The randomized PARTNER I Trial produced the most conclusive evidence of safety and effectiveness of the Edwards SAPIEN THV in high surgical risk (Cohort A) and inoperable (Cohort B) patients with severe, symptomatic aortic stenosis [23,24]. The PARTNER II trial demonstrated safety and effectiveness of the second and third generation valves, the SAPIEN XT THV and SAPIEN 3, respectively, in intermediate risk, high risk and inoperable patients [25,26].

### **5. Characteristics, structure and composition, operating principle, mechanism of action, and test range of product**

## 5.1 Product characteristics

### SAPIEN 3 Transcatheter Heart Valve

The Edwards SAPIEN 3 Transcatheter Heart Valve (Figure 1) is indicated for use in patients with severe, symptomatic, calcified aortic stenosis.

The Edwards SAPIEN 3 transcatheter heart valve (THV) is comprised of a balloon-expandable, radiopaque, cobalt-chromium alloy frame, trileaflet bovine pericardial tissue valve, and polyethylene terephthalate (PET) fabric skirt. It is treated according to the Edwards ThermaFix process, and is packaged and terminally sterilized in glutaraldehyde.

Figure 1. SAPIEN 3 Transcatheter Heart Valve (THV)

## 5.2 Structure and composition, operating principle, mechanism of action of product

The SAPIEN 3 THV is provided with the Commander Delivery System and other components. Table 1 summarises the components that may be provided in the kit.

Table 1. SAPIEN 3 THV Commander Kit

Product Name	20 mm System	23 mm System	26 mm System	29 mm System
	Model/REF			
Kit	S3TF120	S3TF123	S3TF126	S3TF129
Edwards SAPIEN 3 Transcatheter Heart Valve	9600TFX20 (20 mm)	9600TFX23 (23 mm)	9600TFX26 (26 mm)	9600TFX29 (29 mm)
Commander Delivery System^1	9610TF20	9610TF23	9610TF26	9610TF29

Edwards Expandable Introducer Sheath Set (“eSheath”)	9610ES14	9610ES14	9610ES14	9610ES16
Edwards Transfemoral Balloon Catheter	9350BC16	9350BC20	9350BC23	9350BC25
Crimper	9600CR	9600CR	9600CR	9600CR
Inflation Devices (x2)	96402	96402	96402	96406
 Includes a Loader, Qualcrimp Crimping Accessory, and 2-piece Crimp Stopper				

### Commander Delivery System

The Edwards Commander Delivery System consists of a balloon catheter for deployment of the THV and a Flex Catheter to aid in valve alignment to the balloon, tracking and positioning of the THV. The delivery system includes a tapered tip to facilitate crossing of the aortic valve. The handle contains a FlexWheel to control flexing of the Flex Catheter, and a Balloon Lock and Fine Adjustment Wheel to facilitate valve alignment and positioning of the valve within the aortic annulus. A stylet is included within the guidewire lumen of the delivery system. The Balloon Catheter has radiopaque Valve Alignment Markers defining the working length of the balloon. A radiopaque Center Marker in the balloon is provided to help with valve positioning. A radiopaque Triple Marker proximal to the balloon indicates the Flex Catheter position during deployment.

### Expandable Introducer Sheath Set

The Edwards eSheath Introducer Set is intended for introduction of interventional devices in the vascular system. The product is intended for use by physicians trained and experienced in interventional techniques. Standard techniques for placement of vascular access sheaths should be employed.

### Edwards Transfemoral Balloon Catheter

The balloon catheter is indicated for dilation of stenotic native aortic valve leaflets.

### Loader

The loader (packaged with the Edwards Commander delivery system) is used to aid insertion of the delivery system into the sheath, and may be removed to utilize the full working length of the inserted device

### Crimper

The crimper reduces the diameter of the THV to mount it to the delivery system. The crimper is comprised of a compression mechanism that is closed with a handle located on the housing. The crimper is used with a 2-piece crimp stopper (packaged with the delivery system) to correctly crimp the THV.

### Qualcrimp

The Qualcrimp crimping accessory (packaged with the Qualcrimp delivery system) is used during crimping of the THV.

### Inflation Device

An inflation device with locking mechanism may be used during native valve predilation and THV deployment.

### 5.3 Trial range

The THV is intended to be implanted in a native annulus size range comparable to the following measurements:

Table 1. SAPIEN 3 Annulus and Valve Sizing

Native Valve Annulus Size (TEE)	Native Valve Annulus size (CT)		THV size
	Area	Area Derived Diameter	
16-19 mm	273-345 mm 	18.6-21.0 mm	20 mm
18-22 mm	338-430 mm 	20.7-23.4 mm	23 mm
21-25 mm	430-546 mm 	23.4-26.4 mm	26 mm
24-28 mm	540-683 mm 	26.2-29.5 mm	29 mm

## 6. Indications of products and contraindications, and matters needing attention

These devices must always be used according to the current Instructions for Use (IFU) provided with each product

### Indications

The Edwards SAPIEN 3 valve, Edwards Commander delivery system and accessories are indicated for use in patients with severe, symptomatic, calcific aortic valve stenosis who are considered at high risk for surgical valve replacement

### Contraindications

Use of the Edwards SAPIEN 3 valve with the Edwards Commander delivery system and accessories is contraindicated in patients with:

- Evidence of intracardiac mass, thrombus, vegetation, active infection or endocarditis
- Inability to tolerate anticoagulation/antiplatelet therapy

## 7. Overall design

### 7.1 Trial design

#### 7.1.1 Trial purpose

The purpose of this trial is to evaluate the safety and effectiveness of the SAPIEN 3 transcatheter heart valve implantation (TAVI) in Chinese patients with symptomatic severe calcific aortic stenosis who are considered at high risk for surgical valve replacement. Clinical data will be submitted for the purposes of obtaining Chinese regulatory approval.

### 7.1.2 Selection of test methods and reasons

This is a prospective, single-arm, multi-center study to assess the safety and effectiveness of the SAPIEN 3 THV. Up to 60 patients will be enrolled and implanted with the device at four sites in China over an estimated six-month enrolment period with a follow-up period to 5 years. The study is expected to last 5.5 years.

An Echocardiography Core Lab will be established for standardizing echocardiographic secondary endpoints. A Medical Reviewer will review all endpoint-related adverse events.

### 7.1.3 Measures for reducing and avoiding bias

An independent Echocardiography Core Lab will be established for standardizing echocardiographic secondary endpoints. A Medical Reviewer will review all endpoint-related adverse events independently.

### 7.1.4 Selection of subjects (including selection of control group if necessary)

To ensure that a minimum of 50 patients are implanted with the SAPIEN 3 THV and complete the 30 Day follow-up for Primary Endpoint, up to 60 patients will be enrolled and implanted with SAPIEN 3 THV. Each site may not contribute more than 25 implanted patients to the study population. All patients will be followed for 5 years.

Enrolment will be closely monitored to ensure not more than 60 patients are implanted with SAPIEN 3 THV.

#### 7.1.4.1 Inclusion Criteria

Patients must meet all of the Inclusion Criteria in order to participate in the study

1. Subjects who are considered to be operable and high risk for surgical valve replacement: STS Score  $\geq 8$  and  $\leq 15$  or Logistic EuroSCORE  $\geq 15$  and  $\leq 40$ . If STS Score is below 8 and Logistic EuroSCORE is below 15, patients should have other clinical or anatomical risk factors that would be considered high risk for surgery and documented by the heart team
2. Severe symptomatic calcific aortic stenosis requiring aortic valve replacement characterized by one or more of the following within 60 days prior to the index procedure: AVA  $< 0.8 \text{ cm}^2$ , Indexed AVA  $< 0.5 \text{ cm}^2/\text{m}^2$ , mean gradient  $> 40\text{mmHg}$ , or peak aortic jet velocity  $> 4.0\text{m/sec}$ .
3. NYHA Functional Class II or greater.
4. The study patient or the study patient's legal representative has been informed of the nature of the study, agrees to its provisions and has provided written informed consent as approved by the EC of the respective clinical site.
5. The study patient agrees to comply with all required post-procedure follow-up visits.
6. Native aortic valve annulus area between  $273 \text{ mm}^2$  -  $683 \text{ mm}^2$  as measured by CT.
7. Native aortic annulus diameter between 18.6 mm – 29.5 mm as measured by CT.

#### 7.1.4.2 Exclusion Criteria

Patients must not meet any of the Exclusion Criteria in order participate in the study

1. Evidence of an acute myocardial infarction  $\leq$  1 month (30 days) before the intended treatment [(defined as: Q wave MI, or non-Q wave MI with total CK elevation of CK-MB  $\geq$  twice normal in the presence of MB elevation and/or troponin level elevation (WHO definition)].
2. Aortic valve is a congenital unicuspid or is non-calcified.
3. Aortic valve is bicuspid and the patient is less than 60 years old, or the aortic valve is bicuspid with no raphe (Sievers classification type 0)
4. Anomalous coronary artery that would interfere with proper placement of the valve.
5. Mixed aortic valve disease (aortic stenosis and aortic regurgitation with predominant aortic regurgitation  $>3+$ ).
6. Pre-existing mechanical or bioprosthetic valve in any position.
7. Any therapeutic invasive cardiac procedure resulting in a permanent implant that is performed within 30 days of the index procedure. Implantation of a permanent pacemaker or ICD is not considered exclusion criteria.
8. Any patient with a balloon valvuloplasty (BAV) within 30 days of the procedure (unless BAV is a bridge to procedure after a qualifying echocardiogram).
9. Leukopenia (WBC  $<$  3000 cell/mL), acute anemia (Hgb  $<$  9 g/dL), Thrombocytopenia (Plt  $<$  50,000 cell/mL).
10. Renal insufficiency (creatinine  $>$  3.0 mg/dL) and/or renal replacement therapy at the time of screening.
11. Untreated clinically significant coronary artery disease requiring revascularization.
12. Emergency interventional/surgical procedures within one month (30 days) prior to the TAVI procedure.
13. Hypertrophic cardiomyopathy (HCM with myocardium more than 1.5cm without an identifiable cause) with or without obstruction (HOCM).
14. Severe ventricular dysfunction with LVEF  $<$  20%.
15. Echocardiographic evidence of intracardiac mass, thrombus or vegetation.
16. Active upper GI bleeding within 3 months (90 days) prior to procedure.
17. A known contraindication or hypersensitivity to all anticoagulation regimens, or inability to be anticoagulated for the study procedure.
18. Stroke or transient ischemic attack (TIA) within 3 months (90 days) of the procedure.
19. Estimated life expectancy  $<$  12 months (365 days) due to carcinomas, chronic liver disease, chronic renal disease or chronic end stage pulmonary disease.
20. Significant aortic disease, including marked tortuosity (hyperacute bend), aortic arch atheroma [especially if thick ( $>$  5 mm), protruding or ulcerated] or narrowing (especially with calcification and surface irregularities) of the abdominal or thoracic aorta, severe “unfolding” and tortuosity of the thoracic aorta.
21. Iliofemoral vessel characteristics that would preclude safe placement of the introducer sheath.
22. Currently participating in an investigational drug or another device study. Note: Trials requiring extended follow-up for products that were investigational, but have since become commercially available, are not considered investigational trials.
23. Active bacterial endocarditis within 6 months (180 days) of procedure, with or without treatment.

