#### 7.1.5 Patient Screening and Data Collection

##### 7.1.5.1 Patient Screening and Enrolment

The study site shall have a committed Heart Team involved in the screening process. The Heart Team will include at least two cardiac surgeon, one interventional cardiologist, one radiologist, and one anesthesiologist but could also include (without being limited to) the following specialties:

- Echocardiography
- Gerontology

The screening of patients in cardiovascular and cardiac surgery departments will be conducted by one or more delegated study team members. The study team will be responsible for ensuring and reporting study patient screening for study eligibility. Cumulative screening and enrollment logs will be maintained by study sites. Reasons for screen failures will be documented in study logs.

To accommodate the implant procedure learning curve, a roll-in strategy will be available. Each study site will be allowed up to two roll-in patients. Edwards Lifesciences will document if the patient is a roll-in patient before the implant procedure begins. Roll-in patients will complete all study visits and procedures, and not be counted toward the 60 implanted patients.

In addition, the Heart Team will be required to assess all patients for study inclusion to ensure compliance to surgical risk criteria, screening procedures to assess valve size and delivery method, and other inclusion/exclusion criteria. After heart team identifies a patient, the Sponsor will review and confirm eligibility during the case review process.

All patients who sign a study informed consent will be entered into the database. Subjects will be included

in analysis of the trial if an Edwards' investigational device is inserted into the patient. Only patients that leave the procedure room with a SAPIEN 3 THV in place will be counted toward the 60 implanted patients.

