#### 7.1.5.2 Data Collection

Study subjects will undergo screening and pre-procedure visits, and then follow-up visits at Discharge, and 30 Days (+14 days) for Endpoint analysis. Long-term follow-up data is collected at 6 Months (+/- 30 days), 1 Year (+/- 60 days), 2 Years (+/- 60 days), 3 Years (+/- 60 days), 4 Years (+/- 60 days), and 5 Years (+/- 60 days).

The Study Visit Schedule is outlined in Table 4 for enrolled subjects for the duration of the study from Screening and Baseline through the 30 Day visit (Primary Endpoint) and 5 year follow-up visits.

Table 2. Study Visit Schedule

	Screening	(≤30 days of procedure) Baseline	Procedure	Post-Procedure (Within 48 hours)	Discharge	30 Day Follow-Up (+14 days)	6 Month (+/-30 days)	1 Year (+/-60 days)	2-5 Years (+/-60 days)
Informed Consent	X								
Medical History	X								
Physical Exam	X				X	X		X	X
CSS Angina	X				X	X		X	X
NYHA Classification	X				X	X		X	X
STS Risk Score, Logistic EuroSCORE, and EuroSCORE II	X								
Operability Risk Assessment	X								
Cardiac Medications		X	X	X	X	X	X	X	X
Adverse Event Assessment			X	X	X	X	X	X	X
Frailty Assessment		X							
NIH Stroke Scale		X 		X 	X 	X 			
Modified Rankin Scale		X 		X 	X 	X 			
Six Minute Walk Test (6MWT)		X 				X 			
KCCQ Questionnaire		X				X			
Labs									

Hemoglobin, Hematocrit, Platelet Count and White Blood Cells		X		X	X	X			
PTT or PT/INR		X		X	X				
CK/CK-MB and/or Troponins		X 		X 		X			
Creatinine		X		X	X	X			
Liver Panel (ALT, AST)		X							
Albumin		X				X			
Non-Invasive Tests									
ECG		X		X	X	X		X	
Chest X-ray		X							
Transthoracic Echocardiogram (TTE)	X				X	X		X	X
Fluoroscopic imaging implanted valve			X			X 		X 	X 
Invasive Tests									
CT Thoracic/Abdomen with visualization of iliac and femoral arteries	X								
Cardiac Catheterization or CT angiogram	X								
Supra-aortic Angiogram or (TEE)	X		X						
Invasive hemodynamics			X						

 Collection of adverse events begins when the patient starts the procedure. This is defined as when anesthesia is first administered

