## Baseline

Assessments and laboratory tests are required to be completed within 30 days prior to the procedure date. Assessments and laboratory tests completed outside of the 30 days will need to be repeated. If completed outside of standard of care, then a Patient Informed Consent Form will need to be signed first.

The following Baseline data will be collected for all study patients prior to procedure:

- Current cardiac medications and all medications given for cardiovascular effect;
- Neurological assessment
  - National Institutes of Health Stroke Scale (NIHSS) (Appendix C)
  - Modified Rankin Scale (mRS) (Appendix D)
- Frailty Assessment (Appendix E)

- Six Minute Walk Test (Appendix F)
- Kansas City Cardiomyopathy Questionnaire (KCCQ) (Appendix G)
- Clinical Laboratory Tests
  - Blood count (hemoglobin, hematocrit, platelet count, white blood cells)
  - PTT or PT/INR
  - CK/CK-MB and/or Troponins
  - Creatinine
  - Liver Panel (ALT, AST)
  - Albumin
- Non-invasive studies
  - 12-Lead ECG
  - Chest x-ray

Procedure

Transfemoral access technique will be used by the investigator in his/her normal practice of interventional cardiology and patient selection process.

Recommended Antiplatelet/Anticoagulation Regimen

Table 4 outlines the recommended antiplatelet regimen. The categories were developed by The PARTNER II Trial Patient and Procedure Management Steering Committee. There are no current validated guidelines in this specific study population, however, the literature was surveyed and used as guidance for the following proposed guidelines. It is expected that specific agents and dosing regimens may vary from site to site. Patients will be assessed by the heart team for Category of Stroke Risk prior to prescribing treatment regimen. The Category and specific treatment regimen will be documented in the discharge case report form. Committee Categories are based on CHADS 2 score for stroke risk [27].

NOTE: The CHADS 2 score only applies to patients in atrial fibrillation (AF) and has not been validated in non-AF patient populations; therefore the CHADS 2 score reference was used as one among many guidelines to establish the risk stratification for intensity of anticoagulation regimen.

Table 3. Summary of Recommended Antiplatelet/Anticoagulation Therapy

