## 7.3 Monitoring Plan

Edwards Lifesciences will contract with a Contract Research Organization (CRO) to provide a Clinical Research Associate(s) (CRA) to monitor the study sites to ensure that all investigators are in compliance with the protocol and the Investigator's Agreement, and that all study subjects have been properly consented with the current version of the informed consent document. Edwards Lifesciences will evaluate circumstances where an investigator deviates from the clinical protocol and will retain the right to remove either the investigator or the investigational site from the study.

Routine on-site monitoring visits shall include verification of the following:

- Compliance with the protocol, any subsequent amendment(s), GCP and maintenance of regulatory and EC requirements. Deviations shall be discussed with the Investigator(s) or delegated personnel, documented and reported
- Only authorized and delegated individuals are participating in the study
- The SAPIEN 3 THV System is being used according to the protocol and IFU
- Study Site resources, equipment and study personnel, remain adequate throughout the duration of the study
- Patient Informed Consent is completed in accordance to the protocol and regulations
- Only Patient Informed Consents Forms approved by the EC are used appropriately
- Source documents and other clinical records are accurate, complete up to date, stored and maintained properly
- CRFs and queries are complete, recorded in a timely manner, and consistent with source documents
- All adverse events and device deficiencies are reported to Edwards without unjustified delay
- All serious adverse events and deviations are reported to the EC, if required

- All other required reports, notifications, applications, submissions and correspondence are maintained in the investigator's files and are accurate, complete, timely, legible, dated and identify the clinical investigation
- Current laboratory normal values, laboratory certifications, accreditations, or other validations are present in the investigator's file
- Subject withdrawal has been documented; the monitor shall discuss this with the principal investigator or his/her authorized designee
- Subject non-compliance with the requirements stated in the informed consent has been documented; the monitor shall discuss this with the principal investigator or his/her authorized designee

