## **14. Provisions on deviation from clinical trial protocol and correction of clinical trial protocol**

The investigator will not deviate from the protocol without the prior written approval of Edwards Lifesciences except in medical emergencies or in unforeseen, isolated instances where minor changes are made that will not increase the patient's risk or affect the validity of the trial. In medical emergencies, prior approval for protocol deviations will not be required, but the Edwards Lifesciences clinical research personnel must be notified within 24 hours of the incident.

All protocol deviations need to be recorded in the respective section of the eCRF and reported according national and ethics committee requirements. Periodic monitoring of protocol compliance will be performed for each site. The sponsor maintains the right to place a moratorium on enrollment in sites deemed to have excessive protocol compliance issues. A major protocol violation is the instance where a deviation significantly affects the integrity of the study and guidelines for Good Clinical Practice, such as when there is failure to obtain informed consent or violation of inclusion/exclusion criteria. In cases of major protocol violation, the principal investigator is required to make a written statement attesting to retraining or other action(s) to be

taken at his/her site to avoid such violations in the future.

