## **15. Direct access to source data and files**

### Records

All records related to the study and qualifications of site personnel must be kept on file and available for review. These documents may include but are not limited to:

- Clinical trial investigational plan and all amendments, all approved versions
- Signed clinical trial agreement
- EC approval letter, including final informed consent
- EC membership list
- Correspondence relating to the trial
- CVs for all investigators and research coordinator
- Site personnel signature list
- Clinical monitor sign-in log
- Patient screening/enrollment log
- Lab certification and lab test normal ranges
- Reports (includes reports from investigator and sponsor)

All records related to the patients' consent and study data must be maintained for each patient enrolled in the trial. These records include and are not limited to:

- Signed Patient Informed Consent Form (latest approved site version)
- All completed eCRFs
- Supporting documentation of any complications and/or safety events.

Edwards Lifesciences requests that the investigator retain copies of procedure reports, procedure nursing notes and the results of any interventional procedures that occurs post trial procedure. Edwards Lifesciences reserves the right to secure data clarification and additional medical documentation on patients enrolled in this trial.

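### Exclusion 9 gives its white-cell and platelet limits per mL (3/µL and 50/µL); read literally these exclude no realistic candidate, subject to a source check for a lost micro sign

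*Combined protocol and SAP*

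**What the plan says.** Section 7.1.4.2 bars any patient who meets one of its 23 exclusion criteria. Criterion 9 pairs three named conditions with three numeric limits:

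- Leukopenia: white cells below "3000 cell/mL), acute anemia (Hgb" (the quote runs on into the anemia limit).
- Acute anemia: hemoglobin below "9 g/dL), Thrombocytopenia (Plt" (the quote runs on into the platelet limit).
- Thrombocytopenia: platelets below 50,000, again in cells per mL.

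The counts appear elsewhere only as tests to be done. The visit schedule in section 7.1.5.2 lists "Hemoglobin, Hematocrit, Platelet Count and White Blood Cells", and the Baseline list has "Blood count (hemoglobin, hematocrit, platelet count, white blood cells". The Post-Procedure, Discharge and 30-Day lists do the same. None of these gives a unit or a limit.

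Three other provisions bear on how the criterion is applied. Under section 7.1.5.1 the Heart Team assesses each patient and then "the Sponsor will review and confirm eligibility during the case review process". Section 7.3 has monitors verify that the investigator's file holds "Current laboratory normal values, laboratory certifications, accreditations", and section 15 keeps "Lab certification and lab test normal ranges" on file. Section 14 gives as examples of a major protocol violation "failure to obtain informed consent or violation of inclusion/exclusion criteria".

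**The concern.** A limit attached to a named condition should pick out patients who have that condition. A limit per mL is 1000 times lower than the same number per µL, and at that level the white-cell and platelet limits appear to pick out nobody. The named condition and its number would then give opposite answers for the same patient: someone with a plainly low platelet count has thrombocytopenia by name but is far above the stated limit.

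What is at stake is consistent eligibility. The Heart Team, the sponsor's case review and the monitor could each apply the literal number, a silently corrected unit or the local laboratory's normal range, and these can disagree. Because section 14 treats breach of an exclusion criterion as a major violation, the text should settle whether enrolling such a patient is a breach. At present it does not.

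**Working it through.** **Inputs from the documents (section 7.1.4.2, criterion 9).** White-cell limit 3000 per mL; platelet limit 50,000 per mL. These are stated thresholds, not derived figures, so there is no calculation in the plan to reproduce.

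**Conversion.** 1 mL = 1000 µL, so limit per µL = limit per mL / 1000.

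- White cells: 3000 / 1000 = 3/µL, or 0.003 x10^9/L.
- Platelets: 50,000 / 1000 = 50/µL, or 0.05 x10^9/L.

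**Comparison with low counts.** The documents give no patient counts, so the counts here are assumptions. Ratio = assumed count per µL / limit per µL.

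| Measure | Assumed count (/µL) | Written limit (/µL) | Ratio | Excluded as written? |
|---|---|---|---|---|
| White cells | 100 | 3 | 33.3 | No |
| White cells | 500 | 3 | 166.7 | No |
| White cells | 1000 | 3 | 333.3 | No |
| Platelets | 1000 | 50 | 20 | No |
| Platelets | 5000 | 50 | 100 | No |
| Platelets | 10,000 | 50 | 200 | No |

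Across these assumed counts the ratios run from 20 to 333.

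**Sensitivity to the assumed counts.** Milder counts lie further above the limits. A platelet count of 20,000/µL gives 20,000 / 50 = 400. Counts just under the same numbers read per µL (2999 and 49,999) give 2999 / 3 = 999.7 and 49,999 / 50 = 1000.0. No count tried is excluded as written; all of them would be if the same numbers were per µL. The factor of 1000 between the two readings does not depend on any assumed patient. The per-µL reading is shown only to size the discrepancy.

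**Search for a correction elsewhere.** Sections 7.1.5.1, 7.1.5.2 (schedule and visit lists), 7.3 and 15 neither restate the limits nor give a unit for these counts. Criterion 9 is the only source for the cut-offs.

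**Possible reading fault.** No micro sign appears anywhere in the supplied text. A micro sign that was simply dropped would leave cell/L, so reaching mL needs the sign to be replaced by an m at both places. That can happen with a symbol font, and a systematic substitution would affect both places alike. Other special characters (≥, ≤, cm²) survive in the eligibility criteria. The supplied text therefore does not settle the question.

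**The case against.** The strongest objection is that the error may not be in the protocol. The text was read from PDF by a program, faults of that reading are not faults of the plan, and a micro sign read as m would produce exactly this wording. If the source shows µL, nothing is left. This stands as a limit on confidence and is why the source check comes first. It does not remove the point, because nothing in the supplied text shows a lost character.

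The second objection is that the criterion still works in practice. It names the conditions, its hemoglobin limit is sound, two parties check each case, and laboratory normal ranges are on file. This also stands, and it keeps the practical effect small. Those safeguards let a clinician recognise a low count, but they do not supply the trial's own cut-off.

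Third, no wrong enrolment or wrongly recorded violation has been shown, and on the literal numbers enrolling a patient with a low count breaches nothing. That is correct. What remains is that the named condition points the other way, so the text does not settle the question for a monitor.

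Fourth, the 20- to 333-fold range depends on the counts chosen. That is also correct. The conclusion that nobody is excluded holds over every count tried, and the factor of 1000 needs no assumed count.

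**Conclusion.** The concern holds, as a minor point with medium confidence. Two of the three numeric limits in one exclusion criterion of 23, read as supplied, equal 3 white cells/µL and 50 platelets/µL. They would exclude no realistic candidate and contradict the conditions they are meant to define. The conversion is certain. The statement about realistic candidates rests on assumed counts that are not in the documents. The whole point rests on the source reading mL, which the supplied text cannot confirm. The practical effect is probably small, and the hemoglobin limit, the primary endpoint, its analysis and the sample size are unaffected.

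**What to change.** The sponsor should first look at criterion 9 in the source document. If it shows µL, the point falls away. If it shows mL, the sponsor should reconcile the unit with the named conditions and restate both limits in the unit that the site laboratories report. The same wording should go into the protocol, the eligibility case report form and the sponsor's case-review check. The supplied documents do not show the eligibility form, so whether it needs changing has to be checked. No clinical threshold is proposed here.

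The cost is a look at one line and, if mL is confirmed, a one-line unit correction carried into those places. The analysis and the sample size do not change.
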